### 6.5 **Treatment blinding**

Participants, investigator staff (including OHPs), persons performing the assessments, and the Novartis Clinical Trial Team (CTT) will remain blinded to the identity of the treatment from the time of randomization until database lock except for unblindings listed in Table 6-3.

Unblinding a single participant at site for safety reasons (necessary for participant management) will occur via an emergency system in place at the site. As a result, the participant should be discontinued from the study treatment.

The DMC members will be un-blinded as per the procedures described in the DMC charter.

The randomization codes associated with participants from whom PK samples are taken will be disclosed to PK analysts who will keep PK results confidential until database lock. Randomization codes may be also disclosed to biomarker analysts (concerned with target engagement markers or pathway engagement markers) who also will keep the blind.

The following method will be used to maintain the blind:

the identity of the treatments will be concealed by the use of study treatment that are all identical in packaging, labeling, schedule of administration, appearance, taste, and odor.

At the time of safety review/interim analysis for efficacy, the Novartis CTT may create and review unblinded interim reports.

Table 6-3 Blinding and unblinding plan

Role		Time o	r Event	
	Randomization list generated	Treatment allocation & dosing	Safety event (single subject unblinded)	Interim Analysis & dose escalation
Participants	В	В	UI	В
Site staff	В	В	UI	В
Unblinded site staff (see text for details)	В	UI	UI	UI
Drug Supply and Randomization Office	UI	UI	UI	U
Statistician/statistical programmer/data analysts	В	В	UI	UI
Independent committees used for assessing interim results	В	UI	UI	UI
All other sponsor staff not identified above	В	В	UI	UI
Unblinded sponsor staff (see text for details)	В	UI	UI	UI

B Remains blinded

NA Not applicable

UI Allowed to be unblinded on individual patient level

### 6.6 Dose escalation and dose modification

Investigational dose adjustments and/or interruptions are not permitted.

### 6.7 Additional treatment guidance

### 6.7.1 Treatment compliance

The investigator/site staff must promote compliance by instructing the participant to take the study treatment exactly as prescribed and by stating that compliance is necessary for the participant's safety and the validity of the study. The participant must also be instructed to contact the investigator if he/she is unable for any reason to take the study treatment as prescribed. Compliance will be assessed by the investigator and/or study personnel at each visit using pill counts and information provided by the participant. This information should be captured in the source document at each visit. All study treatment dispensed and returned must be recorded in the Drug Accountability Log.

Off-site treatment compliance will be assessed by the OHP and details of which will be shared with the investigator.

#### 6.7.2 Recommended treatment of adverse events

At present there is insufficient information to provide specific recommendations regarding treatment of adverse events (AEs). If participants experience a deterioration of their PAH condition investigators should determine if they need to be treated with additional PAH directed therapy. Study treatment discontinuation criteria as defined in Section 9.1 should be observed.

### 6.7.3 **Emergency breaking of assigned treatment code**

Emergency code breaks must only be undertaken when it is required to in order to treat the participant safely.

Most often, discontinuation from study treatment and knowledge of the possible treatment assignments are sufficient to treat a study participant who presents with an emergency condition. Emergency treatment code breaks are performed using the IRT. When the investigator contacts the system to break a treatment code for a participant, he/she must provide the requested participant identifying information and confirm the necessity to break the treatment code for the participant. The investigator will then receive details of the investigational drug treatment for the specified participant and a fax or email confirming this information. The system will automatically inform the Novartis monitor for the site and the study team that the code has been broken.

It is the investigator's responsibility to ensure that there is a dependable procedure in place to allow access to the IRT at any time in case of emergency. The investigator will provide:

- protocol number
- name (if available)
- participant number

In addition, oral and written information to the participant must be provided on how to contact his/her backup in cases of emergency, or when he/she is unavailable, to ensure that un-blinding can be performed at any time.

# 7 Informed consent procedures

Eligible participants may only be included in the study after providing (witnessed, where required by law or regulation), IRB/IEC-approved informed consent.

If applicable, in cases where the participant's representative(s) gives consent (if allowed according to local requirements), the participant must be informed about the study to the extent possible given his/her level of understanding. If the participant is capable of doing so, he/she must indicate agreement by personally signing and dating the written informed consent document.

Informed consent must be obtained before conducting any study-specific procedures (e.g. all of the procedures described in the protocol). The process of obtaining informed consent must be documented in the participant source documents.

Novartis will provide to investigators in a separate document a proposed informed consent form that complies with the ICH E6 GCP guidelines and regulatory requirements and is considered appropriate for this study. Any changes to the proposed consent form suggested by the investigator must be agreed by Novartis before submission to the IRB/IEC.

Information about common side effects already known about the investigational treatment can be found in the Investigator's Brochure (IB). This information will be included in the participant informed consent and should be discussed with the participant during the study as needed. Any new information regarding the safety profile of the investigational drug that is identified between IB updates will be communicated as appropriate, for example, via an investigator notification or an aggregate safety finding. New information might require an update to the informed consent and then must be discussed with the participant.

The following informed consents are included in this study:

- Main study consent, which also included:
  - CCI
- As applicable, Pregnancy Outcomes Reporting Consent for female participants or the female partners of any male participants who took study treatment
- CCI

Women of child bearing potential must be informed that taking the study treatment may involve unknown risks to the fetus if pregnancy were to occur during the study and agree that in order to participate in the study they must adhere to the contraception requirements.

Male participants must be informed that if a female partner becomes pregnant while he is enrolled in the study, contact with the female partner will be attempted to request her consent to collect pregnancy outcome information.

A copy of the approved version of all consent forms must be provided to Novartis after IRB/IEC approval.

The study includes the option for the participant to have certain study procedures performed off-site by an off-site healthcare professional instead of at the study site, for which a separate signature is required if the participant agrees. It is required as part of this protocol that the Investigator presents this option to the participant, as permitted by national and local governing regulations. The process for obtaining consent should be exactly the same as described above for the main informed consent.

Guidance issued by local regulatory bodies on this aspect prevail and must be implemented and appropriately documented (e.g. the presence of an impartial witness, sign/dating separate ICFs by trial participant and person obtaining informed consent, etc.).

## 8 Visit schedule and assessments

The Assessment Schedule (Table 8-1) lists all of the assessments when they are performed. All data obtained from these assessments must be supported in the participant's source documentation.

Participants should be seen for all visits/assessments as outlined in the assessment schedule (Table 8-1) or as close to the designated day/time as possible. Missed or rescheduled visits should not lead to automatic discontinuation.

The following visits may be conducted at an off-site location as allowed by local laws and regulations: Visit 120 (Week 9), Visit 140 (Week 17), Visit 150 (Week 21), and Visit 199 (Week 29).

For all visits, assessments may occur throughout the visit window over multiple days, as needed, except where defined. For Day 1 and Week 25 visits with timed PK draws, only PK samples need to be taken post-dose.

On clinic visit days, the participant should take LTP001 during the clinic visit prior to post-dose PK samples (when applicable), when instructed by the study staff. RHC assessments and 6 minute walk test assessments should be executed at approximately the same time after drug administration each time (+/- 1 hour).

Participants who discontinue from study treatment are to return for the end of treatment visit as soon as possible, and attend the follow-up visits as indicated in the Assessment Schedule.

Participants who discontinue from study or withdraw their consent/oppose the use of their data/biological samples should be scheduled for a final evaluation visit if they agree, as soon as possible, at which time all of the assessments listed for the final visit will be performed. At this final visit, all dispensed investigational product should be reconciled, and the adverse event and concomitant medications not previously reported must be recorded on the eCRF.

[figure not shown]
The "X" in the table denotes the assessments to be recorded in the clinical database or received electronically from a vendor. The "S" in the table denotes the assessments that are only in the participant's source documentation and do not need to be recorded in the clinical database.

Table 8-1 Assessment Schedule

Period	Screening						Т	reatr	nent								EOS
Visit Name	Screening 2				Trea	tment								EC	т		EOS 
Visit Numbers 	1		100					12 0	13 0	14 0	15 0			16	0		1999
Days	-56 to -1		1					57 +5	85 +5	11 3 +5	14 1 +5			16 +			199 ±5
Weeks	-8 to -1			1			5	9	13	17	21			2	5		29
Time (post- dose)	-	Predos e	0mi n	15mi n	45mi n	120mi n	-	-	-	-	-	-	0mi n	15mi n	45mi n	120mi n	-
Informed consent 21	Х																
Inclusion / Exclusion criteria	Х	Х															
Demography	Χ																
Medical history/current medical conditions	x																
Physical Examination	S						S³										S 
Lung Function Testing	X 																
Body Height	Х																
Body Weight	Х	Х					Χ	Χ	Χ	Χ	Χ	Χ					X
Body Temperature	Х	Х					Х	Х	Х	Х	Х	Х					Х
Blood Pressure and Pulse Rate	Х	Х					х	Х	Х	Х	Χ	Х					Х

Period	Screening						Т	reati	ment	 							EOS
Visit Name	Screening 2				Trea	atment								EC	Т		EOS 
Visit Numbers 	1			100			11 0	12 0	13 0	14 0	15 0			16	0		1999
Days	-56 to -1		1					57 +5	85 +5	11 3 +5	14 1 +5			16 +:			199 ±5
Weeks	-8 to -1			1			5	9	13	17	21			2	5		29
Time (post- dose)		Predos e	0mi n	15mi n	45mi n	120mi n	-	-	-	-	-	-	0mi n	15mi n	45mi n	120mi n	-
Electrocardiogra m (ECG)	Х	Х					Х	Х	Х	Х	Х	Х					X
CCI																	
emPHasis-10 	X 	X 8					X9	X9	X9	X9	X9	X 9					
PAH-SYMPACT 	X 9	X 9					X 	X9	X 	X 	X 	X 9					
Dose administration 			Х				Х	Х	Х	Х	Х		Х				
Drug dispensation		S					S	S	S	s	S						
Collect study medication/ perform drug accountability 							S	S	S	S	S	S					
Pregnancy and assessments of fertility	S	S 					s	S	s	s	s	S					S
Hematology	X 	Х					Χ	Χ	Χ	Χ	Χ	Χ					X
Clinical Chemistry	X 	Х					Х	Х	Х	Х	Х	Х					Х

Period	Screening						Т	reatr	ment	t							EOS		
Visit Name	Screening 2		Treatment											EC	Т		EOS 		
Visit Numbers 	1	100					11 0	12 0	13 0	14 0	15 0	160					1999		
Days	-56 to -1	1				29 +5	57 +5	85 +5	11 3 +5	14 1 +5			16 +:			199 ±5			
Weeks	-8 to -1			1			5	9	13	17	21			2	5		29		
Time (post- dose)		Predos e	0mi n	15mi n	45mi n	120mi n	-	-	-	-	-	-	0mi n	15mi n	45mi n	120mi n	-		
Coagulation Assays	X 	Х					X	Х	Х	Х	Х	Х			·		X		
Urinalysis	X 	Х					Χ	Χ	Х	Х	Χ	Х					X		
NT-proBNP		Х					Χ	Х	Х	Х	Х	Х					X		

Period	Screening						Т	reatr	nent								EOS
Visit Name	Screening 2				Trea	tment								EC	т		EOS 
Visit Numbers 	1		100					11 12 13 14 15 0 0 0 0 0 0							1999		
Days	-56 to -1		1						85 +5	11 3 +5	14 1 +5			16			199 ±5
Weeks	-8 to -1		1 5 9 13 17 21 25												29		
Time (post- dose)	-	Predos e							-	-	-	-	0mi n	15mi n	45mi n	120mi n	-
Echocardiogram	Х	•					Χ		Χ			Χ					
6-Minute Walk Test	X 	9															
Concomitant Medications/ Adverse Events			As required														
Serious Adverse Events		X															
Study completion information		X															

<sup>X Assessment to be recorded in the clinical database or received electronically from a vendor

<sup>S Assessment to be recorded in the source documentation only

<sup>1 Visit structure given for internal programming purpose only

<sup>2 All assessments during screening must be done at the clinic site.

<sup>3 Short physical exam may be employed beginning at Week 5, unless complete physical exam is indicated.

<sup>4 Only to be conducted if historical lung function testing within 24 months of screening is not available.

 

 

PROs to be completed by participants for 7 consecutive day intervals beginning 6 days prior to Day 1 and 7 day intervals around each visit from Weeks 5 to 25. The 7th day of collection for each visit should occur during the Visit Window for Weeks 5 to Week 25.

<sup>9 On clinic visit days, PROs are to be the first assessments performed.

<sup>11 Dosing is daily from Day 1 to Week 25 including all visit and non-visit days.

<sup>12 Collect unused study medication, perform drug accountability (pill count) and document compliance with protocol instructions.

Period	Screening						Т	reatı	nent								EOS
Visit Name	Screening 2		Treatment					EOT									EOS 
Visit Numbers 	1			100			11 0	12 0	13 0	14 0	15 0			16	60		1999
Days	-56 to -1		1			29 +5	57 +5	85 +5	11 3 +5	14 1 +5			16 +!			199 ±5	
Weeks	-8 to -1	1				5	9	13	17	21			25			29	
Time (post- dose)	-	Predos e	0mi n	15mi n	45mi n	120mi n	-	-	-	-	-	-	0mi n	15mi n	45mi n	120mi n	-

<sup>13 As per local requirements (such as United Kingdom investigational sites), Day 1 Predose pregnancy tests can be serum and conducted with the investigator's local lab in order to ensure results are available prior to first dosing. In UK investigational sites, a negative serum pregnancy test must be available no more than 7 days prior to first dosing. Where this is not required, a negative urine pregnancy test must be available prior to dosing on Day 1.

<sup>20 EOS visit may be skipped if participant joins the extension study associated with this protocol.

<sup>14 Must occur 15 or more business days prior to planned randomization.

<sup>15 +/-5 min

<sup>16 +/- 15 min

<sup>17 + 1 h

<sup>19 To be completed within 20 days of randomization (and may occur up to pre-dose on Day 1)

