## 6.2.2 Prohibited medication

Participants should remain stable on their PAH-specific background therapy during the study. Unless there is intolerance to background therapy (PDE5i, prostacyclin analogues and receptor agonists, ERA, and sGC stimulators, refer to Section 6.2.1) should be kept stable during the study. Note that a required change in PAH-directed therapy due to clinical worsening of PAH should result in treatment discontinuation and appropriate management of the participant with the PAH directed therapy as per the investigators discretion and the participant's need.

In terms of treatments required for other conditions or adverse events, there are no known drug interaction signals with LTP001 at the dose level under investigation and participants should be treated as per the discretion of the investigator. Also there are no known pharmacodynamic adverse interactions with other treatments identified as yet.

Drugs which are known to prolong the QT interval are prohibited for use throughout the study duration.

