### 8.4.3 Pregnancy and assessments of fertility

A condom is required for all sexually active male participants to prevent them from fathering a child AND to prevent delivery of study treatment via seminal fluid to their partner up to 24 hours after last study drug administration. In addition, male participants should not donate sperm for the duration of study treatment up to 24 hours after last study drug administration.

All pre-menopausal women who are not surgically sterile will have pregnancy testing. Additional pregnancy testing might be performed if requested by local requirements.

If participants cannot visit the site to have serum pregnancy tests during a Public Health emergency as declared by Local or Regional authorities i.e. pandemic, epidemic or natural disaster, that limits or prevents on-site study visits, urine pregnancy test kits may be used. Relevant participants can perform the urine pregnancy test at home and report the result to the site. It is important that participants are instructed to perform the urine pregnancy test first and only if the test result is negative proceed with the administration of the study treatment. A communication process should be established with the participant so that the Site is informed and can verify the pregnancy test results (e.g., following country specific measures).

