2.7.4 Other safety data

2.7.4.1 **ECG** data

PR, QRS, QT, QTcF, and RR intervals will be obtained from 12-lead ECGs for each participant during the study. ECG data will be read and interpreted (locally).

Categorical Analysis of QTcF (Fridericia's formula) interval data based on the number of participants meeting or exceeding predefined limits in terms of absolute QT or QTc intervals or changes from baseline will be presented. The number and percentage of participants with clinical notable QTcF will be summarized by visit and treatment group and overall. A listing of these participants will be produced (by treatment group). The clinical notable criteria for QTcF (Fridericia's formula) are indicated in Table 2-3.

Table 2-3	Clinical notable criteria for QTcF (Fridericia's formula)
-----------	---

ECG parameter (unit)	Clinically notable range		
Notable value considering newly occurring or worsening cases			
QTcF (msec)	> 500		
QTcF (msec)	> 480 if normal at baseline		
Notable change from baseline			
QTcF (msec)	> 60		

All ECG data will be listed by treatment group, participant and visit/time, abnormalities will be flagged. Summary statistics and graphical presentations (e.g., boxplots) will be provided by treatment and visit/time.

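### No on-treatment ECG has a required time after dosing, so the schedule does not ensure that QTcF is observed near peak exposure

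*Protocol*

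**What the plan says.** **QT restrictions and planned analysis.** Exclusion criterion 15 rules out known long QT syndrome, a family history of it, and current QT-prolonging medication. Section 6.2.2 continues the restriction after entry: "Drugs which are known to prolong the QT interval are prohibited for use throughout the study duration". Protocol Appendix 1 and SAP Table 2-3 set notable QTcF limits (above 500 ms, above 480 ms if normal at baseline, and a rise of more than 60 ms). SAP Section 2.7.4.1 then plans: "The number and percentage of participants with clinical notable QTcF will be summarized by visit and treatment group and overall".

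**Timing.** Protocol Section 8 says: "For Day 1 and Week 25 visits with timed PK draws, only PK samples need to be taken post-dose". It also says: "For all visits, assessments may occur throughout the visit window over multiple days, as needed, except where defined". On clinic visit days "the participant should take LTP001 during the clinic visit prior to post-dose PK samples", where such samples apply, on the instruction of study staff. No order is given between that dose and the ECG or vital signs. Section 8.4.2 specifies single, locally read ECGs and gives no time relative to dose.

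**Table 8-1.** The Day 1 ECG is in the column labelled Predose. Weeks 5 to 21 have a dash in the time row. The Week 25 ECG is in a dashed column immediately before the 0 min column. The row for blood pressure and pulse follows the same pattern.

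**The concern.** LTP001 is first in class and, according to Section 4.5, has been given only to healthy volunteers. If a QTcF effect follows plasma concentration, it is most likely to be seen soon after a dose. The study already samples plasma on Day 1 and at Week 25 to obtain Cmax and Tmax, but it requires no ECG alongside those samples.

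The planned QTcF counts would then be hard to interpret. A table with no notable values could mean that there is no effect, or that the tracings were taken at times when an effect would be small. The schedule does not let a reader tell these apart. This matters beyond the study, because the open-label extension is to be offered only if no safety concern emerges (Sections 3 and 6.1.4).

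**Working it through.** The plan states no figure to reproduce. The check is a count of table cells, followed by an illustration under stated assumptions.

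**Step 1: ECG cells in Table 8-1.**

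| Visit | Time shown | On treatment? |
|---|---|---|
| Screening | none | no |
| Day 1 | Predose | no, drug-free baseline |
| Weeks 5, 9, 13, 17, 21 | dash | yes (5) |
| Week 25 | dash, column before 0 min | yes (1) |
| End of study | dash | no, about 30 days off drug |

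Total: 1 + 1 + 5 + 1 + 1 = 9 ECGs, of which 6 are on treatment. Number required after the dose: 0 of 6. Number in a 15, 45 or 120 min column: 0.

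**Step 2: what a compliant site may do.** At Weeks 5 to 21 the ECG may come before or after that day's dose. At Week 25 the column order suggests an ECG before the dose, and the sentence limiting post-dose work to PK samples permits it. A site that completes all assessments and then gives the dose follows the protocol at every visit.

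**Step 3: what a pre-dose ECG could miss.** The visible text gives neither half-life nor time of peak, and PK text is partly redacted, so both are assumed here. With once-daily dosing and single-exponential decline after the peak,

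ratio = exp(−ln 2 × (24 − tmax) / t½).

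With tmax = 2 h the elapsed time is 22 h:

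| Assumed t½ | Concentration at 24 h as share of peak |
|---|---|
| 6 h | exp(−0.693 × 22/6) = 0.08 |
| 12 h | exp(−0.693 × 22/12) = 0.28 |
| 24 h | exp(−0.693 × 22/24) = 0.53 |
| 48 h | exp(−0.693 × 22/48) = 0.73 |

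The assumed time of peak matters little. Moving tmax from 2 h to 0.25 h changes the 12 h result from 0.28 to 0.25 and the 48 h result from 0.73 to 0.71. The half-life drives the answer, so a pre-dose ECG could miss most of the peak or only a modest part of it.

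**Step 4: a tension at Week 25.** Section 8 also says that right heart catheterization and the 6-minute walk test are done at about the same time after drug administration on each occasion, within 1 hour. Both take place at Week 25. That sits awkwardly with the statement, in the same section, that only PK samples need follow the dose.

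**The case against.** The strongest reply is that untimed does not mean trough, and this is right. A reader might infer that QTcF is checked at the lowest daily exposure. The documents do not support that. The only ECG labelled pre-dose is the drug-free Day 1 baseline. Week 25 is pre-dose by column order, not by label. The other five may fall on either side of the dose. Weeks 9, 17 and 21 may also be off-site, where no visible text holds back the dose. Exposure at the ECG is uncontrolled rather than fixed at its minimum.

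Three other tempting inferences also fail:

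- **No blood pressure is tied to a time after dosing.** Blood pressure is recorded at each walk test (Section 8.3.3; Weeks 5, 13 and 25) and listed among the catheterization measurements (Section 8.3.2), and Section 8 links both procedures to time after drug administration. The gap concerns only the vital signs row of Table 8-1.
- **The 24 h condom rule shows that exposure is low by then.** Section 8.4.3 gives a contraceptive precaution, not a PK result. Women must use contraception until about 30 days after the last dose, and neither duration measures exposure.
- **A drug-placebo QTcF difference is biased towards zero.** SAP Section 2.7.4.1 plans counts, summary statistics, plots and listings, and no estimate of a treatment difference.

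The wider reply is that no QT signal is shown. Section 1.1 reports no significant ECG findings in healthy volunteers, Section 4.5 names no mechanism-related concern, and Section 8.4.4 describes these ECGs as standard Phase 2 monitoring. Section 8.4.2 allows unscheduled ECGs at any time. This limits how serious the point is. It does not remove it, because unscheduled ECGs are discretionary and the planned counts rest mainly on scheduled tracings.

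**Conclusion.** The point holds as a gap in the schedule: 0 of 6 on-treatment ECGs must follow a dose, so observation of QTcF near peak exposure is left to site habit. This rests on the visible text of Section 8, Section 8.4.2 and Table 8-1. Some table rows and PK text are redacted, and that is not counted against the plan.

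The consequence cannot be sized from the documents. The range of about 8% to 73% of peak rests on an assumed peak at 2 h, assumed half-lives of 6 to 48 h and single-exponential decline. Carrying it over to QTcF further assumes that any effect follows plasma concentration without delay. No size of effect in milliseconds can be given. The point is worth acting on because the main correction costs almost nothing and makes analyses that are already planned more informative.

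**What to change.** 1. **Table 8-1.** Keep the Day 1 pre-dose ECG as baseline. Move the Week 25 ECG, blood pressure and pulse to one of the existing post-dose PK times, such as 120 min, chosen with the sponsor's own knowledge of the time of peak. This adds no ECG and no waiting, since participants already stay for the PK draws.
2. **eCRF.** Record the clock time of each ECG and of the doses needed to derive time since dose, at all visits. Section 6.3.2 already has the visit-day dose recorded. The eCRF is not visible, so some of these fields may exist.
3. **SAP Section 2.7.4.1.** Summarise QTcF change from baseline by time since dose, next to the planned counts by visit.
4. **Section 8.** Reconcile, for Week 25, the statement that only PK samples need be post-dose with the statement that catheterization and the walk test are done at a set time after drug administration.
5. **Optional.** Set a post-dose ECG window at the on-site Week 5 and 13 visits. It adds a wait of up to about 2 h, so the sponsor should weigh the burden.

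The cost of items 1 to 4 is amendment wording, possibly one or two time fields, and one more SAP table.
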